This is a single-center, prospective cohort study of subjects undergoing clinically indicated PET/CT MPI, with documented coronary artery disease or an intermediate to high pretest likelihood of coronary artery disease. Following the clinical study, the research study is explained to the subjects. Consenting subjects will return on another day (next calendar day or later) for a repeat stress study with Lexercise or a repeat Lexiscan stress PET. Approximately 50 subjects (not more than 16 patients with normal Rubidium-82 or N-13 ammonia PETMPI, 10 healthy volunteers and 24 patients with reversible perfusion defects) will be enrolled in this study. After successful screening and enrollment, 13 random subjects (8 normal and 5 ischemic) will return for repeat Lexiscan PET, and 37 subjects will return for a Lexercise PET/CT MPI. Lexiscan PET will be performed per standard protocol. For Lexercise, a symptom limited exercise treadmill study with Lexiscan injection at peak exercise is performed. Rubidium-82 or N-13 ammonia will be injected and PET/CT images will be obtained in a list mode acquisition. Images will then be unlisted and myocardial blood flow computed.

Number of Subjects Planned

Approximately 50 subjects will be enrolled into the study.

Main Selection Criteria

Subjects will be eligible if they meet all of the following inclusion criteria and none of the exclusion criteria:

Inclusion criteria:

- Age > 18 years
- Clinically indicated Rubidium-82 or N-13 ammonia PET study
- Ten healthy volunteers recruited using web based advertisements.
- Known coronary artery disease (prior percutaneous coronary intervention, prior coronary artery bypass surgery or Q wave MI on ECG) or intermediate to high pretest likelihood of CAD
- Able to exercise on a treadmill
- Able and willing to provide informed consent to participate in the study

Exclusion criteria:

- Contraindications to exercise stress testing such as
 - unstable angina
 - known severe left main coronary artery stenosis
 - severe or uncontrolled heart failure
 - uncontrolled atrial or ventricular arrhythmias
 - symptomatic hypotension or severe hypertension (systolic blood pressure < 90 or > 200 mmHg, respectively)
 - > 1st degree atrioventricular block in the absence of a functioning pacemaker.
- Contraindications to Lexiscan use such
 - Allergy or intolerance to aminophylline or regadenoson

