Hypothesis 1: Lexiscan will cause further/maximal vasodilation in a subject that is already vasodilated from exercise; therefore, the safety of this protocol needs to be ascertained. Lexiscan is expected to be well tolerated when injected during maximal exercise stress without any increase in major adverse events.

Aim 2: To **assess the image quality** of Lexercise PET compared to Lexiscan.

Hypothesis 2: Image quality as assessed by myocardial count density and heart to liver ratio will be superior with Lexercise compared to Lexiscan. However, misregistration artifacts from upward diaphragmatic creep will be higher with Lexercise compared to Lexiscan.

Aim 3: To compare **relative and absolute PET** with Lexercise compared to Lexiscan PET in identifying CAD.

Hypothesis 3: Lexercise PET offers the advantage of imaging reduced myocardial blood flow from vasoconstriction in diseased territories and maximal vasodilation in normal territories. Therefore, in patients with ischemic scans, the defect contrast on relative will be better with Lexercise compared to Lexiscan PET. We hypothesize that the differences in regional CFR between normal and abnormal territories will be greater with Lexercise compared to Lexiscan.

Significance of the mechanistic questions of this proposal:

The overall goal of this proposal is to evaluate the feasibility, utility and mechanistic underpinnings of a novel protocol incorporating combined maximal symptom limited exercise treadmill test with Lexiscan compared to Lexiscan alone. The combined standard symptom limited exercise stress testing with Lexiscan has several novel clinical and research applications:

1. This protocol provides exercise data (hemodynamic, electrocardiographic and clinical data) combined with high quality PET imaging that is important in patient management.
2. A PET MPI study can be performed with physiological exercise stress using any of the available flow tracers (Rubidium-82, N-13 ammonia, or the new compound BMS747158, an F-18 labeled agent) with minimal radiation exposure to the staff.
3. This protocol makes it feasible to assess both endothelium dependent (exercise) and endothelium independent (Lexiscan) mechanisms affecting MBF.

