	Exercise Stress	Dipyridamole Stress	p Value	Correlation	Significance of Correlation
Summed stress score	9.1 ± 5.7	6.9 ± 5.9	<0.01	0.80	<0.001
Summed rest score	3.4 ± 3.3	3.2 ± 2.8	NS	0.79	<0.001
Summed difference score	5.8 ± 4.7	3.7 ± 4.6	<0.02	0.61	0.001
LV defect size (stress) (%)	19.3 ± 11.5	13.8 ± 13.6	<0.02	0.62	0.001
LV defect size (rest) (%)	8.1 ± 9.4	6.4 ± 6.5	NS	0.57	0.003

Values are mean ± SD.

LV = left ventricle; PET = positron emission tomography.

Myocardial count density of N-13 ammonia was significantly greater with dipyridamole compared to exercise stress. Successful performance of exercise ammonia required coordination between the cyclotron team and the imaging team. The authors concluded that treadmill exercise produces larger and more severe perfusion defects than dipyridamole and may reflect true ischemia.

III. STUDY METHODS

This is a single-center, prospective cohort study of subjects undergoing clinically indicated PET/CT MPI, with documented coronary artery disease or an intermediate to high pretest likelihood of coronary artery disease based on age gender and symptoms as described in the ACC/AHA/ASNC appropriate use criteria for cardiac radionuclide imaging.¹² Following completion of the clinical study, the research study is explained to the subjects. Consenting subjects will return on another day for a repeat stress study with Lexercise or a repeat Lexiscan stress PET. Approximately 50 subjects (not more than 16 patients with normal Rubidium-82 PETMPI and 34 with reversible perfusion defects) will be enrolled in this study. After successful screening and enrollment, 13 random subjects (8 normal and 5 ischemic) will return for repeat Lexiscan PET, and 34 subjects will return for a Lexercise PET/CT MPI, on the next calendar day or within 2 weeks of the clinical Rubidium-82 or N-13 ammonia PET study.

SUBJECT SELECTION

Main Selection Criteria

Subjects will be eligible if they meet all of the following inclusion criteria and none of the exclusion criteria:

Inclusion criteria:

- Age > 18 years
- Clinically indicated Rubidium-82 or N-13 ammonia PET study
- Ten healthy volunteers recruited using web based advertisements.

- Known coronary artery disease (prior percutaneous coronary intervention, prior coronary artery bypass surgery or Q wave MI on ECG) or intermediate to high pretest likelihood of CAD
- Able to exercise on a treadmill
- Able and willing to provide informed consent to participate in the study

Exclusion criteria:

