- d. Exercise induced heart block

a) **Source of subjects and recruitment methods**

Patients will be recruited from the nuclear cardiology laboratory at the Brigham and Women's Hospital. Among them, stable and eligible patients meeting all inclusion and exclusion criteria will be invited to participate in this study and those who provide informed consent will be enrolled. Referring physicians will be informed about the study and asked to discuss the study with their patients being referred for PET myocardial perfusion imaging. Ten healthy volunteers will be recruited for this study using web based advertisements.

IV. SUBJECT ENROLLMENT

a) **Methods of enrollment including procedures for patient registration and or randomization**

The following recruitment methods will be used:

- This is a pilot study of subjects referred for a clinically indicated myocardial perfusion PET study. Majority of the subjects will be recruited from the clinical practices of the Brigham and

Women's hospital. The patients' referring physician will introduce the study to the subjects prior to the clinical PET study and those subjects that are willing to consider the study will be given the written informed consent for the study for review. Subjects' questions will be answered by [name]. There will be no time restriction to sign the consent form or participate in this study. Subjects that express an interest will be evaluated and provided they meet all the inclusion and exclusion criteria, they will be considered for this study.

- On occasion, we may identify subjects with reversible perfusion defects from our clinical Rubidium-82 or N-13 ammonia PET studies. In those instances, physicians requesting myocardial perfusion imaging studies (primary or specialist health care provider) will be contacted personally explaining the purpose of the study. The physicians of those subjects will be asked if they felt comfortable introducing the study to their subjects either verbally during the office visit or through a recruitment letter. If the physician introduces the study verbally, the subject will be asked if they would like to speak with a study physician after their appointment. If they would like to speak with someone, [name] will be notified and she will explain the study to the subject and go over the inclusion and exclusion criteria for the study. If they are interested in participating in the study an appointment will be made for their first visit.

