- Hospital in-patients with request for pharmacologic stress: Attending physicians will be asked if they felt comfortable introducing the study to their subjects that they schedule for in-patient pharmacologic stress myocardial perfusion study verbally during their visit. If the physician introduces the study verbally, the subject will be asked if they would like to speak with a coordinator after the visit. If they would like to speak with someone, the coordinator will be notified and they will explain the study to the subject and go over the inclusion and exclusion criteria for the study. If they are interested in participating in the study an appointment will be made for their first visit.
- Special attention will be paid to enroll women and minorities in the study.
- Ten healthy volunteers will be recruited for this study using web based advertisements. They will all undergo Lexiscan (regadenoson) followed by Lexercise protocol (exercise + regadenoson) on a separate day.

b) Procedures for obtaining informed consent (including timing of the consent process)

For subjects interested in speaking to a study staff, Study PI, will go over the inclusion and exclusion criteria and will describe the study and procedures to the potential subject over the phone or in person. If the subject qualifies and is interested he/she is encouraged to discuss the study with his/her primary care physician or family members. Upon arrival for the study, the subject will be given a copy of the consent form to read. After the subject has finished reading the consent form, one of the physician investigators will describe the study in detail and answer any questions or concerns

the subject might have. If the subject agrees to participate in the study they will be asked to provide his/her written informed consent. Subjects will be given a copy of the signed consent form for their records. The investigator will inform the subject that they have the alternative not to participate in the study and can withdraw their consent at any point during the study.

The subjects will be given as much as 2 weeks to consider participation in the trial. Pregnant women and minors are excluded from this trial. Subjects that are determined by the physician to be unable to consent due to their physical or mental condition will not be enrolled in this trial.

V. STUDY PROCEDURES

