The patient will have 1-2 study visits and healthy volunteers will have 2-3 study visits. Study visit 1 is the same for patients and healthy volunteers.

a. Study visit 1

- a. The subjects that are interested in the study will meet with [name] and go over the consent form and details of study participation.
- b. This screening visit will take about 1 hour. The research study team will ask the subject questions about medical history, medications, and prior hospitalizations to make sure that the subject qualifies for this study. Blood pressure, heart and breathing rates, temperature, and height and weight will be measured. Pregnancy is not allowed due to the unknown risks radioactivity may have on the mother or the unborn baby from the beginning of the study period through the end of the study. A blood pregnancy test will be performed on the day of the PET scan in women with child bearing potential.

Patients:

a. Study visit 2

The study visits 1 and 2 can be conducted on the same day. Study visit 2 is for the performance of the Lexercise stress Rubidium-82 or N-13 ammonia PET study. This will be scheduled at least the next calendar day or within 2 weeks of the clinical Rubidium-82 or N-13 ammonia PET study. While we aim to conduct the research scan within 2 weeks of the clinical scan, if there is a scanner malfunction or patient schedule conflict, we would like to extend the time frame for enrollment to 4 weeks.

Approximately 20 cc of blood will be drawn following completion of the Rubidium-82 or N-13 ammonia imaging study and evaluated for biochemical markers of ischemia.

b. Study Visit 3

Study visit 3 is for the performance of the Lexercise stress Rubidium-82 or N-13 ammonia PET study. This will be scheduled at least the next calendar day or within 2 weeks of the clinical Rubidium-82 or N-13 ammonia PET study. Approximately 20 cc of blood will be drawn following completion of the Rubidium-82 or N-13 ammonia imaging study and evaluated for biochemical markers of ischemia. A part of this blood sample (10 cc) will be sent to the laboratory of [name] for the isolation of microRNAs involved in angiogenesis and vascular inflammation. This blood sample will be stored for future analysis.

Healthy volunteers:

a. Study visit 2

The study visits 1 and 2 can be conducted on the same day. Study visit 2 is for the performance of the rest and regadenoson stress Rubidium-82 or N-13 ammonia PET study. No blood drawing will be performed during this visit.

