Rubidium-82 or N-13 ammonia PET image acquisition:

Following skin preparation and ECG lead placement, patient undergoes a symptom limited standard Bruce exercise treadmill test. At peak exercise (when patient is unable to exercise for more than 1 minute), the treadmill is stopped and patient is immediately positioned on the imaging table. Image acquisition is started with a CT scout image for positioning the heart (10 mA, AP scout, 9 seconds). Then 0.4 mg of regadenoson is given by intravenous push over 10 seconds followed by 10 ml of normal saline flush. Right after the saline flush, 40-60 mCi of Rubidium-82 or 20 mCi of N-13 ammonia is injected and emission imaging started in a list mode fashion started at the time of injection of radiotracer. Following completion of the emission imaging, a CT transmission scan (20 mA, 120 KV, non-gated, free tidal breathing) is obtained for correction of photon attenuation by soft tissues. .

Rest and Lexiscan stress images from the clinical study and the Lexercise stress emission images will be unlisted for analysis into a static file, a gated file and dynamic image frames (36 frames of 5 seconds each, 8 frames of 15 seconds each, and 6 frames of 30 seconds each for stress and 2 groups for rest of 24 frames at 5 seconds each and 8 frames at 30 seconds each). In subjects with serious or bothersome adverse effects, aminophylline will be administered intravenously (1 mg/kg, to a maximum of 150 mg) to alleviate the symptoms.

Myocardial blood flow quantification:

Myocardial blood flow (in ml/gm/min) at rest and after vasodilator stress will be quantified using a software based on GFADS and a 2 compartment model, developed and validated at the Brigham and Women's Hospital.¹³ Rest and peak stress myocardial blood flow will be computed in ml/gm/min and global and regional (vascular territories assigned as described below) coronary flow reserve computed by dividing stress myocardial blood flow by rest myocardial blood flow. Coronary vascular resistance at rest and stress will be computed by dividing mean aortic pressure [derived as 2 (diastolic blood pressure) + systolic blood pressure/3] by myocardial blood flow. In addition to calculating the myocardial blood flow for the left ventricle as a whole, myocardial blood flow will be determined for each of three vascular beds

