- Sub diaphragmatic activity (liver heart ratios)
- Defect contrast
- Signal to noise ratio and
- Dynamic image evaluability will be assessed

VI. BIOSTATISTICAL ANALYSIS

The overall aim of this pilot study of 50 patients is to assess the tolerability, safety, diagnostic accuracy and image quality between Lexiscan with symptom limited exercise compared to Lexiscan alone.

Aim 1. For this aim, we will compare the reported side effect profile for Lexercise to Lexiscan PET, using a Pearson Chi square test. A P-value of <0.05 will be considered significant.

Aim 2: For this aim, we will compare objective measures of image quality including signal to noise ratio using dynamic Rubidium-82 images or N-13 ammonia, the frequency of misregistration between PET and CT, the frequency of presumed motion artifact and bowel radiotracer activity. These measures will be compared using a student's t-test or a Pearson Chi square test, as appropriate. A P-value of <0.05 will be considered significant.

Aim 3: For this aim, we seek to compare measures of semi quantitative relative perfusion, absolute perfusion and LVEF using the Lexiscan alone compared to Lexercise PET. Firstly, we will compare semi-quantitative defect size, severity and reversibility between the Lexercise and Lexiscan PET studies. Based on the results of one prior study using N-13 ammonia and comparing dipyridamole versus treadmill exercise², a sample size of 35 subjects with reversible defects should be adequate to identify if significant differences exist between Lexercise and Lexiscan PET protocols. Next, we will study the changes in LVEF from rest to peak stress in Lexercise versus Lexiscan PET studies in the normal and ischemic subjects. Finally, we will compare regional rest and peak stress myocardial blood flow and coronary flow reserve between Lexercise and Lexiscan PET studies.

VII. RISKS AND DISCOMFORT

Time: Participation in this trial entails an exercise vasodilator stress Rubidium-82 PET or N-13 ammonia scan. The total time spent for the study procedures is approximately 1 hour.

Intravenous line insertion: Possible side effects intravenous line insertion are pain, bruising, or infection where the needle entered the skin. Some people faint or get dizzy during insertion of the intravenous line.

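### Aim 3 takes its Lexiscan comparator from the clinical scan that classed the patients and always came first, and the repeat-Lexiscan group has no stated analysis role

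*Combined protocol and SAP*

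**What the plan says.** **Comparison.** Section VI, Aim 3 (and the synopsis statistical plan) states: "we will compare semi-quantitative defect size, severity and reversibility between the Lexercise and Lexiscan PET studies". No test, pairing or model is given for Aim 3.

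**Comparator images.** Section V, image acquisition: "Rest and Lexiscan stress images from the clinical study and the Lexercise stress emission images will be unlisted for analysis".

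**Classification.** Patients enter after a clinically indicated PET. Section III counts them as "not more than 16 patients with normal Rubidium-82 PETMPI and 34 with reversible perfusion defects"; the synopsis gives at most 16 normal patients, 24 with reversible defects and 10 volunteers. Section IV adds that "we may identify subjects with reversible perfusion defects from our clinical Rubidium-82 or N-13 ammonia PET studies".

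**Order.** Patients return for the research scan after the clinical study. Of the volunteers, Section IV says "They will all undergo Lexiscan (regadenoson) followed by Lexercise protocol (exercise + regadenoson) on a separate day". No text counterbalances the order.

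**Repeat scans.** The synopsis and Section III both state that "13 random subjects (8 normal and 5 ischemic) will return for repeat Lexiscan PET". Neither the endpoint list nor any aim in the statistical plan mentions these scans.

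**Hypothesis.** Hypothesis 3 in Section II expects that "in patients with ischemic scans, the defect contrast on relative will be better with Lexercise compared to Lexiscan PET".

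**Rest scan.** For patients, Section V says "Study visit 2 is for the performance of the Lexercise stress Rubidium-82 or N-13 ammonia PET study", with no research rest scan; volunteers have rest and stress imaging at their visit 2. The lower research radiation dose for patients in Section VII (2.7 against 6.9 mSv) fits this.

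**The concern.** One noisy measurement does two jobs: it decides who counts as ischaemic, and it is the baseline from which the Lexercise change is measured. Patients classed as ischaemic include some whose clinical scan overstated their defect; a second scan would on average be smaller even with no protocol difference. Patients classed as normal include some whose scan understated it, so their second scan would on average be larger. Lexercise is always that second scan.

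In ischaemic patients the pull is against Hypothesis 3, so a null result would be hard to read. In normal-scan patients it can look like defects that only Lexercise finds. Volunteers share the fixed order but are not selected on the scan. If strata were combined, the two pulls would offset to an unknown degree.

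A randomly chosen group scanned twice with Lexiscan is the standard way to expose this. The design contains one; the analysis text does not use it.

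**Working it through.** The plan gives no figure for retest drift, so there is none to reproduce. What follows is illustrative.

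**Inputs from Table 3 (N-13 ammonia study, rationale for Aim 3)**
- Summed stress score (SSS): 9.1 ± 5.7 exercise, 6.9 ± 5.9 dipyridamole, correlation 0.80.
- Summed rest score (SRS): 3.4 ± 3.3 and 3.2 ± 2.8, correlation 0.79.
- Summed difference score (SDS), dipyridamole: 3.7 ± 4.6.

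**Assumptions, not in the documents**
- The dipyridamole SDS distribution stands in for Lexiscan and is treated as normal.
- A patient is ischaemic if SDS ≥ 2.
- Stress-scan error equals rest-scan error and is independent of it.
- Both SDS values use the clinical rest scan.

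**Step 1. Check the table.** SD of the SSS difference = √(5.7² + 5.9² − 2×0.80×5.7×5.9) = 3.67. At n = 26, t = 2.2 ÷ (3.67/√26) = 3.05, p = 0.005, in line with the printed <0.01.

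**Step 2. Retest error.** The SRS row compares rest with rest in two studies a median of 6 days apart. Difference SD = √(3.3² + 2.8² − 2×0.79×3.3×2.8) = √4.13 = 2.03. Error variance per scan = 4.13/2 = 2.07 (SD 1.44). Implied SDS retest correlation = 1 − 2×2.07/4.6² = 0.80.

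**Step 3. Drift with no protocol effect.** a = (2 − 3.7)/4.6 = −0.370. With a shared rest scan only the stress error regresses.
- Ischaemic: φ(a)/(1 − Φ(a)) = 0.578; drift = −(2.07/4.6)×0.578 = −0.26.
- Normal scan: φ(a)/Φ(a) = 1.047; drift = +(2.07/4.6)×1.047 = +0.47. This is less reliable because scores stop at 0.

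**Step 4. Sensitivity in ischaemic patients.** With half the error variance in the shared rest scan, drift = −½(1 − r)×4.6×0.578:

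| Retest r | Drift, shared rest | Drift, separate rest |
|---|---|---|
| 0.95 | −0.07 | −0.13 |
| 0.80 | −0.27 | −0.53 |
| 0.60 | −0.53 | −1.06 |

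**Step 5. Effect on power.** With a shared rest scan the SRS cancels, so the SDS difference equals the SSS difference and the SSS row applies (2.2 points, SD 3.67). Ischaemic Lexercise pairs: 24 − 5 = 19 (synopsis) or 34 − 5 = 29 (Section III). Paired t, two-sided 0.05, noncentral t:

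| Pairs | No drift | r = 0.95 | r = 0.80 | r = 0.60 |
|---|---|---|---|---|
| 19 | 69% | 67% | 58% | 47% |
| 29 | 88% | 86% | 78% | 66% |

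**Step 6. What the repeat scans can show.**
- Five ischaemic repeats, SD 2.03: 95% half-width = 2.776×2.03/√5 = 2.5 points.
- Lexercise against repeat Lexiscan, 19 vs 5: SE = √(3.67²/19 + 2.03²/5) = 1.24 with the retest SD from Step 2, or 3.67×√(1/19 + 1/5) = 1.85 with equal SDs. Power for 2.2 points is about 37% (Welch) and 21%.

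**Step 7. Why one effect over strata will not do.** With equal variances, a common effect weights each stratum roughly by n₁n₂/(n₁+n₂): ischaemic 19×5/24 = 3.96, normal-scan 8×8/16 = 4.00. An effect of 2.2 confined to ischaemic patients would come out near 2.2×3.96/7.96 = 1.09, about half.

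**The case against.** **Pairing is inferred.** Aim 3 names no test, and its wording could cover the repeat scans. If second scans were compared between the Lexercise and repeat-Lexiscan groups, regression and order would affect both alike. This stands as a limit; the image-acquisition sentence favours the within-patient reading but does not settle it.

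**The image list is not exhaustive.** It also omits the volunteers' research Lexiscan images, which are clearly meant for use. A reader might infer that the repeat images will go unanalysed. The documents support only that no analysis is stated. A figure after the synopsis statistical plan is not shown and might depict the design.

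**Pooling is not declared.** Hypothesis 3 concerns ischaemic scans, the sample-size sentence concerns reversible defects, and LVEF is to be studied in normal and ischaemic subjects. A reader might infer that the plan pools strata for the defect comparison. It does not say so; it only fails to rule it out. No defect hypothesis is stated for normal-scan patients.

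**The bias is small and conservative where it matters most.** A drift of 0.26 compares with a paired standard error of 3.67/√19 = 0.84, and it is worked out for SDS, not for defect contrast or regional flow reserve. This stands and limits the weight of the point.

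**The check is weak.** A half-width of 2.5 cannot detect a drift of 0.26. True; the repeat scans can expose only a large shift.

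**Conclusion.** The point holds as a should-fix on analysis. The stated comparator is the classifying scan, the order is fixed, and the only concurrent control has no stated use. Under the assumptions listed, the drift is about −0.26 SDS points in ischaemic patients and +0.47 in normal-scan patients. At r = 0.80 it costs about 10 to 11 percentage points of power. At r = 0.95 it is minor.

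A reader might infer that this design would produce a false positive for Hypothesis 3. The documents do not support that: regression runs against the hypothesis in ischaemic patients, so a positive result there is conservative on that account. The order effect could go either way, and nothing in the documents gives its sign or size. Nor should the 69% be charged to this point; power without drift is a sample-size matter. The cited 2.2-point difference may itself contain similar drift.

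Confidence is medium: the structure is plain in the text, but the pairing is inferred and the size rests on stand-in data.

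**What to change.** 1. **Section V, image acquisition:** add the repeat-Lexiscan images and the volunteers' research Lexiscan images to those analysed.
2. **Section VI, Aim 3 and the synopsis:** state that the Lexercise-minus-Lexiscan contrast is paired and analysed separately in ischaemic patients, normal-scan patients and volunteers, with ischaemic patients as the Hypothesis 3 analysis.
3. Beside it, report by stratum the mean repeat-Lexiscan change with 95% confidence interval and limits of agreement.
4. As an exploratory analysis in patients, compare second scans (Lexercise against repeat Lexiscan) adjusted for the clinical-scan value, within each stratum or with a protocol-by-stratum interaction. Do not report one effect pooled over strata.
5. State which rest scan enters each SDS.
6. Name regression to the mean and fixed order as limits on interpretation.

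The cost is a few sentences and the reading of 13 scans already planned, with no added patients or imaging. The downside is precision: the repeat-scan results are descriptive and cannot fix the size of the protocol effect. The patient visit text, which describes only Lexercise at visits 2 and 3, and the differing Lexercise counts (37 in the synopsis, 34 in Section III) need separate reconciliation.
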